1.2 F3. Global Patient Perception of Cognitive Change

A single-item assessing patient's overall perception of their memory problems using a 5-point Likert scale, participants will be asked "Compared to 4 weeks ago, have you noticed that your memory and thinking are:" with responses of much better, somewhat better, about the same, somewhat worse, or much worse.

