Participants will be instructed to take one tablet and 1 capsule (total of 2) of blinded study medication once a day, orally, for 8 weeks. They will start with a Mirabegron (25mg) or tolterodine tartrate (4 mg) dose of study medication and will have the option of dose escalation to 2 tablets and 2 capsules (total of 4) per day (Mirabegron 50mg or tolterodine tartrate 4 mg + identical placebo).

- Mirabegron (25 mg or 2 X 25 mg) with participant-directed dose adjustment
- Detrol LA (4mg or 4mg + placebo) with participant-directed dose adjustment

E2.b Study Medication Supply

Mirabegron (Myrbetriq), tolterodine tartrate (Detrol LA) and placebo tablets identical to the tolterodine tartrate tablets administered in the study will be supplied by Astellas, shipped to the UCSF Pharmacy, and labeled by the pharmacist with randomization numbers. Because the two treatments cannot be made identical, the study will use a double-dummy methodology with the placebo identical to the tolterodine tartrate but these will not be identical to the Mirabegron. Specific procedures for shipping, storing, labeling, logging and returning study medication and for dispensing study medication to participants will be described in detail in the Operations Manual.

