The daily voiding diary period is defined as follows: "Awake Time" begins from the time the subject starts her day (time arose) until she goes to bed for that day. "Bed Time" is defined as the time the subject went to bed until she awoke to start the next day.

E5. Evaluation Schedule

Time of Visit	Tele-phone	SV	Base line	2wk phone	4wk	8wk	ET
Telephone Screening	X						
Information & Informed Consent		X					
3-day voiding diary Instruction		X					
Demographics		X					
Alcohol and Tobacco Use		X					
Medical History		X					
Mini-Mental Status Exam (MMSE)*		X					
Geriatric Depression Scale (GDS)*		X					
Concomitant Medication		X					
Dipstick urinalysis		X				X	X
PVR assessment		X				X	X
Voiding diary Review			X		X	X	X
Height^ and Weight			X			X	
Vital Signs		X	X		X	X	X
Health and Medications Update			X	X	X	X	X
Inclusion/Exclusion/Randomization			X				
Dispense study medication			X		X		
California Verbal Learning Test – Short Form (CVLT-SF)			X			X	X
Digit Span			X			X	X
Trail Making Test Parts A & B			X			X	X
Digit Symbol Substitution Task (DSST)			X			X	X
Pittsburgh sleep quality index (PSQI)			X			X	X
Epworth Sleepiness Scale (ESS)			X			X	X
Physical Function and Mobility: Short Physical Performance Battery (SPPB)			X			X	X
IADL			X			X	X
OAB-questionnaire			X			X	X
Patient Perception of Cognitive Change				X	X	X	X
Adverse events (self-report)				X	X	X	X

Patient Perception of Bladder Condition				X	X	X	X
Participant directed Dose Adjustment				X	X		
Assess study medication compliance				X	X	X	X
Trial medication return/count					X	X	X
Early Termination Report							X
Participant Satisfaction						X	X

[^] Height only at baseline visit

* The MMSE and the GDS will be used only as screening tests to determine eligibility, not as outcome measures

E6. Study Visits

The 8-week RCT requires 2 telephone visits (Telephone Screening, Week 2 Phone Call) and 4 in-clinic visits (Screening, Baseline, Week 4, Week 8 (or Early Termination) visit).

E6.1 Recruitment Phase

Women will be recruited by (1) direct, community-based efforts using large media (newspaper notices, television ads, etc.) and small media (brochures in local businesses, talks to local community, notices in churches, salons etc.); (2) seeking referrals from physician's offices (specifically in urology, urogynecology, gynecology, primary care, and geriatric medicine) and (3) purchasing targeted mailing lists.

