1.1.5 E6.5 Follow-up Visits

E6.5.a Week 2 Phone Call

At Week 2 participants will be contacted via telephone and asked if they want to stay on the current dose of medication or increase the dose at the start of Week 3. Participants will be asked if there have been any changes in their health or medications and reminded to complete the voiding diary just prior to their Week 4 clinic visit. The coordinator will administer two assessments over the phone: the Patient Perception of Cognitive Change and the Patient Perception of Bladder Condition (PPBC).

E6.5.b Week 4

At Week 4 participants will be seen at the clinic and return the voiding diary. Study medication compliance/ accountability and changes in health will be assessed. Participants will be asked if they want to stay on the current dose of medication, or increase/decrease the current dosage. Participants will be asked to bring to the visit all prescription and non-prescription medications that they are currently taking and these will be recorded. Study medication will be dispensed. The coordinator will administer two assessments: the Patient Perception of Cognitive Change and the Patient Perception of Bladder Condition (PPBC).

E6.5c Week 8 (or Early Termination)

At Week 8 participants will be seen at the clinical centers to repeat the dipstick analysis, return the voiding diary, repeat the baseline questionnaires, and the End of Study Questionnaire or Early Termination Report. Weight and vital signs will be obtained. Study medication compliance/ accountability, changes in health and medical resource use (MD visits, surgery, and medications) will be assessed. Participants will be asked to bring to the visit all prescription and non-prescription medications that they are currently taking and these will be recorded.

F. STUDY MEASURES

The clinical assessments used in this study are accurate, reliable, and relevant. Variability is possible in the participant-reported measurements, such as study participants diaries and questionnaires that depend heavily on the participant's understanding of and compliance with protocol instructions. To minimize this possibility, case report forms will be clear and easy to

use, study site staff will be fully trained to administer the instruments, and instructions will be carefully and clearly explained to study participants, both in writing and verbally.

F1. 3-day Voiding diary

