SA 3: Standard chi-square tests will be used to determine differences in report of adverse events at week 8.

SA 4: Number and proportion of participants reporting much better, somewhat better, about the same, somewhat worse and much worse memory and thinking since study enrollment will be calculated. Chi-square test for trend will be used to determine differences patient perception of cognitive change at week 8.

SA 5: ANCOVA will be used to estimate the preliminary differences and calculate the standard deviation of change in incontinence episode frequency measured on the 3-day diary between the Mirabegron and standard anticholinergic therapy groups at week 8, controlling for baseline.

M. NONADHERENCE, STUDY DRUG DISCONTINUATION AND EARLY STUDY DISCONTINUATION

All participants will be encouraged to take all doses of study medication unless safety is a concern. Study coordinators will ascertain reasons for nonadherence to study medication and attempt to help participants find ways to improve adherence. However, participants who are nonadherent with study medication will be urged to attend all study visits and complete all study measurements as planned. Adherence with study medication will be measured by tablet counts at each clinic visit.

Study drug will be discontinued in any participant who has any serious adverse event that, in the judgment of the clinical site investigator, is possibly related to treatment with study medication. Study medication may be resumed if, in the opinion of the clinical site investigator, the abnormal symptom, physical finding or test has been satisfactorily evaluated and found to be benign.

Participants will be considered to have permanently discontinued study medication if they report not taking study medication for 4 weeks or longer. In this case, study termination measurements will be obtained if possible.

All participants will be urged to attend all study visits and complete all study measurements as planned. However, participants can discontinue participation in the study at any time. Participants who miss a visit will be contacted by the study coordinator to reschedule the visit and to provide assistance in completing the visit. Participants who state that they no longer desire to participate in the trial will undergo study termination measurements if possible.

N. REFERENCES

1. Mitteness LS. The management of urinary incontinence by community-living elderly. *Gerontologist* 1987;27:185-93.

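### Section L reports perceived cognition as change since enrolment, but with the F3 stem the Week 8 answer covers only weeks 4 to 8

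*Combined protocol and SAP*

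**What the plan says.** Section F3 defines a single five-category item on memory and thinking, with the stem "Compared to 4 weeks ago, have you noticed that your memory and thinking are". It gives no other wording for any visit.

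In the E5 evaluation schedule, the row "Patient Perception of Cognitive Change" is marked at the Week 2 call, Week 4, Week 8 and early termination (ET), but not at Baseline. The E6.5 visit narrative names the item at Week 2 and again at Week 4: "The coordinator will administer two assessments: the Patient Perception of Cognitive Change and the Patient Perception of Bladder Condition (PPBC". The Week 8 narrative does not name it, although E5 marks it there.

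Section L, under SA 4, has two sentences on this item. The first lists the five response categories and ends "somewhat worse and much worse memory and thinking since study enrollment will be calculated", without naming a visit. The second reads "Chi-square test for trend will be used to determine differences patient perception of cognitive change at week 8".

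Section C names global patient perception of cognitive function under SA2, as one of two cognitive measures for which a standard deviation is wanted. Specific Aim 4 in Section C is patient satisfaction.

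**The concern.** The item and its analysis use different reference points: four weeks before the visit in F3, study enrolment in Section L. Nothing in the document reconciles them. With no baseline administration, change since enrolment cannot be recovered by subtraction.

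Perceived cognition is a named SA2 outcome, and the trial exists to prepare a larger comparison of cognitive effects. A Week 8 table headed as change since enrolment would describe only the second half of treatment. A null Week 8 test could then be read as no perceived effect of treatment, although the four weeks in which both drugs are started were not tested.

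**Working it through.** No sample-size or power figure bears on this point, and Section K states that no power analysis was done. The check compares recall windows.

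**Inputs.** Recall period: 4 weeks (F3). Assessment weeks: 2, 4 and 8 (E5). Treatment: 8 weeks from randomization (Section E). Enrolment is taken as randomization, week 0, because Section L under SA 1 pairs the two words. The Baseline Visit follows screening by 1 to 2 weeks (E6.4).

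**Formula.** At visit week t the stem covers week t − 4 to week t. A statement about change since enrolment needs week 0 to week t.

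| Visit | Window of the stem | Window of the Section L label | Same start? |
|---|---|---|---|
| Week 2 | 2 − 4 = −2, so −2 to 2 | 0 to 2 | No; 2 of the 4 weeks precede randomization |
| Week 4 | 4 − 4 = 0, so 0 to 4 | 0 to 4 | Yes |
| Week 8 | 8 − 4 = 4, so 4 to 8 | 0 to 8 | No; 4/8 = 50% covered |

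The ET window depends on the date of termination and has no fixed entry.

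**Sensitivity to the meaning of enrolment.** If it meant the Screening Visit, the period at Week 8 would be 8 + 1 = 9 to 8 + 2 = 10 weeks. Coverage would be 4/9 = 44% to 4/10 = 40%. The label fails at Week 8 on either reading.

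**What this does to an answer.** Take a woman who notices a decline in weeks 0 to 4 and is stable afterwards. A correct answer is in a worse category at Week 4 and the unchanged category at Week 8. Under the enrolment label, her Week 8 answer could be reported as no change since enrolment. The reverse can also happen: a woman who declines early and then recovers correctly reports improvement at Week 8, although she may be no better than at enrolment. The documents do not say how many women of either kind to expect, so neither the size nor the direction of the distortion can be computed.

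**What the planned analysis leaves out.** The Week 4 answer is the only scheduled one for which stem and label agree, and Section L assigns it no test. The two ordinal answers cannot be added to give a net 8-week rating. Nor does the Section L text on this item produce the standard deviation that SA2 asks for.

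**The case against.** Several points can fairly be made for the plan.

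- *F3 does not state that the same stem is used at every visit.* This stands. The Week 8 narrative refers to an end-of-study questionnaire whose wording is not given, so the Week 8 wording cannot be confirmed. The conclusion holds for the stem as stated, which is the only wording in the document.
- *The sentence with the enrolment label names no visit.* This also stands, and it is why the mislabelling could occur rather than must. Week 8 is the only visit named in that part of Section L, so it is the natural reading. The label would also fail at Week 2.
- *Randomization protects the comparison.* A reader might infer that the Week 8 test is invalid, or biased toward no difference. The documents do not support that. The between-arm test is valid for perceived change over weeks 4 to 8; it answers a narrower question than the label suggests.
- *Dose changes might be thought to make matters worse.* A reader might argue that the optional increase is active in one arm ("Mirabegron (25 mg or 2 X 25 mg) with participant-directed dose adjustment") and placebo in the other ("Detrol LA (4mg or 4mg + placebo) with participant-directed dose adjustment"), so the late window favours one drug. This feature runs through the whole trial, and a change made at Week 4 would also fall inside a window running from enrolment to Week 8. It does not separate the two reference points and adds nothing here.
- *It is one item in a pilot, and early decline is recorded at Week 4 anyway.* This is correct and limits the severity. It does not make the label right, and the recorded Week 4 answer has no planned comparison.

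**Conclusion.** Wrong as written; severity minor. With the F3 stem, the Week 8 answer covers 4 of the 8 weeks since randomization and cannot support a statement about change since enrolment. The one scheduled answer that could describe change from randomization, at Week 4, is collected but not tested.

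The conclusion assumes that the stem is used unchanged at Week 8, that visits occur at their nominal weeks, and that enrolment means randomization. The last assumption does not affect the result at Week 8.

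The consequence is confined to this item. The neuropsychological battery is measured at baseline and Week 8, analysed with adjustment for baseline, and unaffected. The size of any distortion cannot be calculated from the documents, and no claim is made that a treatment effect would be missed.

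**What to change.** **If the item is already in use**, keep the stem and change Section L:

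- Delete the reference to study enrolment.
- Report the response distribution and the standard deviation required by SA2, by arm, at Week 4 (labelled change from randomization to Week 4) and at Week 8 (labelled change from Week 4 to Week 8). State the numeric scores given to the five categories.
- Apply the chi-square test for trend at both visits. Name Week 4, before unblinding, as the main comparison for the effect of starting treatment, and Week 8 as secondary.
- List ET answers separately, because their window depends on the termination date.
- Make no claim of change since enrolment from this item.
- Place the analysis under SA2. Section L's SA 4 entry will then need its own sentence on patient satisfaction, which is what Specific Aim 4 covers.

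**If the item is not yet in use**, the alternative is to anchor the stem to the time before study medication was started, as F8 does with its pre-intervention reference, and keep the Week 8 test.

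**Cost.** The first option needs a few sentences and one extra trend test on data already collected. Section L states no significance level. At an assumed 0.05 per test, the chance of at least one false positive over two tests is at most 2 × 0.05 = 0.10 (1 − 0.95² = 0.0975 if they were independent), which is why one visit is named as main. The alternative costs a one-line wording change and an 8-week recall period at Week 8 in women aged 65 and over. Either is a protocol amendment needing approval under Section I1; neither adds visits or participants.

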1.3 F4. Depression

Validated self-administered questionnaire, the Geriatric Depression Scale (GDS)²³ will be used as an exclusionary tool at the Screening Visit and will gather additional information about major depression. *Participants must score < 6 to qualify for the study.*

F5. Sleep

Pittsburgh Sleep Quality Index (PSQI)

The Pittsburgh Sleep Quality Index (PSQI)^{24,25} measures reported sleep patterns and sleep problems, including sleep quality, sleep latency, sleep efficiency and napping behavior. The PSQI is an 18-item questionnaire that has been demonstrated to have high internal consistency (0.83), test-retest reliability (0.85) and diagnostic validity. A global sleep quality score derived from the PSQI can be used to index overall quality of sleep over the prior one-week period. Global sleep quality scores are continuous (range 0-21) with high scores reflecting poor sleep quality. It will be administered at Baseline and Week 8 (or Early Termination) visits.

Epworth Sleepiness Scale (ESS)

The Epworth Sleepiness Scale (ESS) is a simple, self-administered questionnaire measuring general level of daytime sleepiness.²⁶ The ESS is a 8-item questionnaire that has been demonstrated to have a sensitivity of 94% and a specificity of 100% in distinguishing excessive daytime sleepiness from normal daytime sleepiness.²⁷ The questionnaire assesses the level of general sleepiness during eight real life situations on a 0-3 scale; possible scores range from zero to 24, and higher scores reflect greater sleepiness. The PSQI and ESS are stable measures of sleep quality and sleepiness over the past year in early middle-aged adults.²⁸

1.4 F6. Physical Function and Mobility

Measured with Short Physical Performance Battery (SPPB) and Instrumental Activities of Daily Living (IADL) (same as used in the Health and Retirement Study). ²⁹ Clinically significant change includes new difficulty in I-ADL or worsening on the Short Physical Performance Battery (includes chair stand, balance, gait speed).²⁹

F7. Overactive Bladder Questionnaire (OAB-q)

OAB-q is a self-administered, 33-item, validated questionnaire that assesses how much the subject has been bothered by selected bladder symptoms during the previous week.³⁰ It consists of two distinct components. The first 8 questions comprise the symptom bother score. Questions 9-33 comprise the health-related quality of life (HRQOL) component, which includes the domains of coping, concern, sleep, and social interaction. Higher scores represent better quality of life. It will be administered at Baseline and Week 8 (or Early Termination) visits. Participants are not allowed to look at previously completed assessments.

1.5 F8. Global Rating of Patient Satisfaction and Perceptions of Improvement

Two validated questions assessing patient's satisfaction with the intervention and perception of improvement of their bladder problems will be administered: ³¹

- Patient satisfaction question (PSQ): How satisfied are you with your progress in this program? With responses of Completely, Somewhat, or Not at all
- Global perception of improvement (GPI): Overall, do you feel that you are: Much Better, Better, About the same, Worse, or Much worse. This is compared to pre- intervention (so there is no baseline value).

F9. Other Measurements

Weight will be recorded in kilograms using a calibrated scale. Participants will be measured in light clothing (without shoes) to the nearest 0.5 kg. Standing height, which is measured at the baseline visit only, will be measured in centimeters with a calibrated wall-mounted Harpenden

stadiometer or ruler. Variables that may act as predictors of the frequency of incontinence will be documented at screening or baseline. These covariates include demographic characteristics (age, race/ethnicity, residency location (independent, assisted), relationship status, education), general health, genitourinary history (duration of incontinence, prior type and duration of therapy, amount of urine loss, pad use, drinking habits), smoking behavior, reproductive health (gravity, parity, route of delivery, menopause status, hormone therapy use), medical history/comorbidities (hypertension, cardiovascular disease, pulmonary disease, stroke, diabetes) surgical history (hysterectomy, pelvic organ prolapse repair, other pelvic or abdominal surgery), history of falling on past month, and medications.

G. DATA MANAGEMENT

G1. Data Collection

A secure study database will be developed using the UCSF Research Electronic Data Capture system (REDCap). REDCap enables researchers to create on-line databases for input, cleaning, management, and exporting of all study data. The study programmer analyst, who has previously used REDCap to create study databases for large multi-centered studies, will create a REDCap database unique to our study. REDCap also contains advanced features for data cleaning, importing, and embedded calculated database fields and is supported by the UCSF Information Technology Service.

All study data from each site will be entered into the HIPAA-compliant REDCap database using on-line study forms. Participants will complete questionnaires on paper which will then be entered by the research assistant into the REDCap study forms which prompts for missing or nonsensical data. Other participant data will also be entered into REDCap study forms. Missing data or incorrect values will be identified instantaneously using cross-checks in the database and research assistants will be asked to address these issues within 24 hours.

H. SAFETY MONITORING PLAN

The conduct of the study and safety of participants will be evaluated by an independent Data and Safety Monitor (DSM), [name], Senior Investigator at Kaiser Permanente of Northern California. [name] is a clinical researcher with experience in clinical trials, research ethics, and statistics. The DSM will periodically review the conduct and outcomes of the study and provide feedback to the investigators, with particular attention to protecting the safety of study participants. The DSM is independent of the institution and the investigators participating in the study and has no financial ties to the outcome of the study.

Prior to initiation of the trial, the DSM will review and approve the study design and plans for recruitment, adherence, interventions, data quality, and safety monitoring. At periodic intervals during the course of the trial, the DSM will evaluate the adequacy and timeliness of participant recruitment, evaluate the ability of the trial to reach stated goals, review adherence to visits and protocols, assess data quality and timeliness, evaluate the safety of participants, provide a report to the investigators and the IRB on the scientific progress of the trial and the safety of participants, make recommendations to the investigators on continuation, termination, or other modifications of the trial, and consider factors external to the study (i.e., new scientific or therapeutic developments) when relevant to the safety of the participants or the ethical conduct of the trial.

The DSM will periodically review aggregate and unblinded trial data after 20 and 40 participants complete the 4-week visit. An emergency meeting may also be called by the principal investigator at any time should questions of participant safety arise. Each review will include an assessment of the adequacy and timeliness of participant recruitment, adherence to the visit and intervention protocols, data quality and timeliness, adverse effects, and participant safety.

Given that the study is of short duration, no assessment of interim efficacy will be done, and the study will not be stopped or altered for unexpected efficacy or lack of efficacy. Interim reports for the DSM will be prepared by an unblinded biostatistician at the Women's Health Clinical Research Center, and sent to the DSM at least 5 days prior to a pre-scheduled review. A copy of the interim reports will be retained in a locked, confidential file by the DSM.

After each interim review, the DSM will provide a signed statement that indicates whether the study should continue, terminate, or be altered based on ability to meet study recruitment and data quality goals and participant safety. He will include any recommendations for changes to the protocol if necessary to enhance participant safety or potentiate the ability of the trial to answer the research hypotheses. This statement will be provided to the principal investigator and will be sent to the UCSF IRB. All materials, discussions, and proceedings of the DSM process will be completely confidential.

I. ETHICS

1.6

